11.3	SUBJECT STIPENDS OR PAYMENTS	36
12	REFERENCES	37
13	ATTACHMENTS	38

List of Abbreviations

AD: Alzheimer's Disease

AE: Adverse Event

BMAA: β -N-methylamino-L-alanine

BMP: Basic Metabolic Panel

CBC: Complete Blood Count

eAD: Early Stage Alzheimer's Disease

GCP: Good Clinical Practice

GMP: Good Manufacturing Practice

GRAS: Generally recognized as safe

IRB: Institutional Review Board

LFT: Liver Function Tests

MoCA: Montreal Cognitive Assessment

NFT: neurofibrillary tangles

SAE: Serious Adverse Event

CDR: Clinical Dementia Rating Scale

Hemoglobin A1C: Hgb A1C

Study Summary

Title	A Phase IIa proof of concept, randomized, double-blind, placebo-controlled study of the effects of L-serine on early stage Alzheimer's disease patients
Short Title	Phase IIa L-serine trial for eAD
Protocol Number	LSPI-2, D16180
Phase	Clinical study Phase IIa
Methodology	Randomized, double-blind, placebo controlled
Study Duration	Approximately 2.5 years
Study Center(s)	Single-center
Objectives	Determine tolerability of L-serine for early stage Alzheimer's disease patients and assess preliminary indications of efficacy.
Number of Subjects	40
Diagnosis and Main Inclusion Criteria	Patients with a clinical diagnosis of early stage Alzheimer's disease.
Study Product, Dose, Route, Regimen	L-Serine 30g / day oral dose of 15 x 1g gummy chews morning and night with an ascending dose for two weeks of 2 x 1g gummies BID, two weeks of 8 x 1g gummies BID, and 246 days of 15 x 1g gummies BID.
Duration of administration	36 weeks
Reference therapy	Placebo, 15 gummies without L-serine morning and night with an ascending dose for two weeks of 2 gummies BID, two weeks of 8 gummies BID, and 246 days of 15 gummies BID.
Statistical Methodology	Non-parametric statistical analysis based on Mann-Whitney U test, with the critical value set at $p < 0.05$.

1 Introduction

This document is a protocol for a human research study. This study is to be conducted according to US and international standards of Good Clinical Practice (FDA Title 21 part 312 and International Conference on Harmonization guidelines), applicable government regulations and Institutional research policies and procedures.

1.1 Background

[figure not shown]
Early stage Alzheimer's disease (eAD) represents a clinical syndrome which encompasses an underlying neuropathological process, beginning with a long asymptomatic period followed by indications of mild cognitive impairment. Clinically this is characterized by cognitive declines with lapses in episodic memory, decline in speed of processing information, difficulty performing tasks, misplacing valuable objects, and a decreased ability to plan or organize activities. At this point, only palliative treatment is available, and no drug has been discovered which can slow the progression of eAD.

The Institute for Ethnomedicine and the Miller School of Medicine Department of Neurology recently were able to produce a model tauopathy with sparse amyloid deposits in a non-human primate, vervets (*Chlorocebus sabaues*) (Cox et al. 2016) which has some aspects similar to Braak 1 early stage Alzheimer's disease pathology (Braak 1995, Cox et al. 2016). These Alzheimer's-type features include neurofibrillary tangles (NFT) formed from misfolded tau as determined by AT8 immunohistological staining and β -amyloid deposits determined by β -amyloid(1-42) immunohistological stain; both of these neuropathological hallmarks of Alzheimer's disease were confirmed with Thioflavine-S IHC staining. Dense NFT were found in brain regions consistent with eAD although they occurred primarily in cortical layer I, rather than cortical layers I-II. The Institute for Ethnomedicine and the Miller School of Medicine Department of Neurology were unable to assess cognitive decline in these animals and so this model at this point in time is based solely on neuropathology. However, it is believed that an increasing density of NFT and β -amyloid plaques in human beings is correlated with cognitive declines in human Alzheimer's patients (Nelson et al. 2012).

The Institute for Ethnomedicine and the Miller School of Medicine Department of Neurology used this non-human primate model to test the naturally-occurring dietary amino acid L-serine and found that dietary supplementation in non-human primates reduced the density of NFT by 35-50% in eight regions of the brain including the amygdala and anterior cingulate gyrus (Cox et al. 2016). L-serine is a naturally-occurring amino acid that is a normal part of the human diet, regarded as GRAS by the FDA with the average American receiving 3.5 grams/day from all sources. Since the Institute for Ethnomedicine and the Miller School of Medicine Department of Neurology have found in replicated studies in non-human primates that supplementing the diet with L-serine results in a decreased density of NFT, we now seek to evaluate the tolerability of L-Serine and the potential of L-serine in slowing cognitive declines associated with early Alzheimer's disease.

1.2 Investigational Agent

L-serine (C₃H₇NO₃; 105.09 g/mol; synonym (S)-2-amino-3-hydroxypropanoic acid) is a naturally-occurring dietary amino acid. It is abundant in soy products, some edible seaweeds, sweet potatoes, eggs, and meat. Since some L-serine is produced by astrocytes in the brain, it is considered a non-essential amino acid. L-serine is directly involved in the biosynthesis of purines, pyrimidines, and other amino acids. Serine residues are found in most proteins and within proteins functions as a site for phosphorylation.

L-serine is considered as GRAS (generally recognized as safe) by the FDA and has been approved as a normal food additive under CFR172.320. It is widely sold as a dietary supplement. An FDA-approved Phase I human clinical trial of L-serine for ALS patients, sponsored by the Institute for Ethnomedicine and conducted by the Phoenix Neurological Associates, has now been published (Levine et al. 2016); patients were found to tolerate well doses up to 30 grams/day (ClinicalTrials.gov identifier NCT01835782). Similarly, Harvard University and Massachusetts General Hospital are conducting a two-year study on L-serine supplementation to correct biochemistry associated with hereditary sensory neuropathy type 1 at doses of 400mg/kg/day which for an average

American of 75.5kg is about 30 grams, the dose which we propose to use in this study (ClinicalTrials.gov identifier NCT01733407).

1.3 Preclinical Data

In human neuronal cell cultures, L-serine blocks misincorporation of β -N-methylamino-L-alanine (BMAA) into neuroproteins, which otherwise leads to protein misfolding, aggregation, and cell apoptosis (see insert: Fig 4 from Dunlop et al. 2013). This protective effect of L-serine was replicated in a non-cell synthesis system, where protein incorporation of BMAA increased when L-serine was removed from the system and when human DNA templates were available in comparison with bacterial DNA templates (Glover et al. 2014). Data on fruit-flies, *Drosophila melanogaster*, reveals that the presence of L-serine decreases the amount of BMAA incorporated into protein by half (Fig. 1, below). In addition, 40% of flies fed BMAA die within three days, however, co-administration with L-serine saves every fly within this time frame (Fig. 2, below).

[figure not shown]
[figure not shown]

Figure 4. Inhibition of incorporation or radiolabel into cell proteins by L-serine. Panel A, Incorporation of radiolabeled BMAA was inhibited by L-serine in a concentration dependent manner. Panel B, D-serine (D-SER) had no significant impact on the incorporation of BMAA (NS, $P = 0.4419$). L-serine significantly inhibited the incorporation of BMAA compared to control cells (CTRL, $***P = 0.0002$) and D-serine (D-SER, $**P < 0.01$). Panel C, there was a significantly ($***P < 0.001$) greater incorporation of BMAA when all protein amino acids were omitted from the culture medium (ALL) compared to when none were (NONE). When only L-serine was omitted (L-SERINE) incorporation was restored to approximately 80% ($****P = 0.0009$). Student's two-tailed T-test, values are mean \pm SD for three independent experiments ($n = 3$).
doi:10.1371/journal.pone.0075376.g004

[figure not shown]
Figure 1: Protein incorporation in fruit flies fed BMAA and co-administered L-serine.

Figure 2: Survival of fruit flies fed BMAA and co-administered L-serine.

(Fig. 2)

(Fig. 1)

Based on these in vitro and in vivo results suggesting a neuroprotective function of L-serine, the Institute for Ethnomedicine and the Miller School of Medicine Department of Neurology supplemented the diet of vervets (*Chlorocebus sabaues*) exposed to BMAA with L-serine for 140 days. In replicated experiments, we found that co-administration of the dietary amino acid L-serine significantly reduced the density of NFT, with greater than 50% reduction in median NFT densities within the temporal (dorsal and ventral), primary motor, and entorhinal (posterior) and insula cortices, and a greater than 35% reduction of NFT density in the perirhinal cortex, amygdala, and anterior singulate cortex (Fig. 3).

[figure not shown]

Figure 3: Reduction of NFT production in vervets fed both BMAA and L-serine (pink:high+SER) in comparison with equal amount of BMAA without L-serine (purple: high). Data from Cox et al. 2016.

1.4 Clinical Data to Date

A phase I human clinical trial for safety of L-serine for ALS patients (NCT01835782) has just been published (Levine et al. 2016). Patients (n=20) were given either 1, 5, 15, or 30 g/day for six months. Very few side-effects were reported (bloating, nausea, and loss of appetite; Levine et al., 2016). Analysis of the ALSFRS-R slopes indicates that ALS patients taking L-serine had a reduction in rate of functional loss compared to historical ALS control patients (5 studies that included patients with symptom duration <3 yrs and FVC \geq 60% to compare with the L-serine patients). There is no evidence of neurological harm to ALS patients as compared to controls. Sample sizes within a dose group are small, and so a Phase II trial of L-serine for 66 ALS patients is planned to see if this preliminary indication of efficacy can be replicated in a larger group. What we can currently conclude is that L-serine at doses up to 30g/ day is safe for ALS patients.

In the Harvard study of 14 subjects with hereditary sensory autonomic neuropathy (HSAN1) L-serine was given at either 200 mg/kg or 400 mg/kg (roughly 15 and 30 g/day respectively) and no adverse effects were reported with either dose after 10 weeks of therapy (Garolfalo et al. 2011).

There are three additional trials currently reported by clinicaltrials.gov involving L-serine: 1) NCT01733407, 400mg/kg/d L-serine, L-Serine Supplementation in Hereditary Sensory Neuropathy Type 1; 2) NCT02528994, 6, 12, 24, or 48 g/day, Short Term Dietary Serine Supplementation and Circulating Serine Levels; 3) NCT02599038, 20 or 200 mg/kg/day, Serine Supplementation for Obese Subjects With Fatty Liver Disease. None of these trials currently have reported data, but it is important to note that trials with L-serine at doses of 30 and 48 g/day are underway.

1.5 Dose Rationale and Risk/Benefits

Since there is no literature as to how much L-serine is tolerated or beneficial in eAD patients, we considered doses generally tolerated by humans in the above reported clinical trials. The dose selected for this trial will be 30g/day as this dose was well-tolerated by both ALS patients and HSAN1 patients. L-serine will be administered orally through gummies being produced in a GMP compliant facility (Knechtel, Chicago, IL). Each gummy contains 1 g L-serine (treatment) and will be packaged in a foil packet containing 15 pieces to be taken both morning and evening (with or without food) for nine months. The placebo will be a gummy with no L-serine, packaged and taken in the same manner.

Although chewing this quantity of gummies, and the dose of 30g/day of L-serine has been well tolerated by other neurological patients, we will monitor side-effects in these eAD patients during a dose ramp-up period. We will also monitor amino acid balances in blood serum samples. In order to assess tolerability in patients, we have designed a 4 week dose ramp-up. Patients will take 2g (BID) for the first two weeks followed by 8g (BID) for the next two weeks. If patients tolerate these doses without negative effects, then they will begin taking 15g (BID) for the remainder of the study. If a patient cannot tolerate either 2 or 8g (BID) they will be dropped from the study, however, if a patient can tolerate 8g (BID) but not 15g (BID), they will remain in the study through an additional 246 day period taking a total of 15g per day (1 package of gummies split into two time periods within the day). The same ramp-up schedule and procedures will be observed for both placebo and L-serine patients.

2 Study Objective

Determine tolerability of L-serine for early stage Alzheimer's disease patients and assess preliminary indications of efficacy. Efficacy will be assessed by cognitive testing and biomarkers in plasma.

3 Study Design

3.1 General Design

This is a Phase IIa, randomized, double-blind, placebo controlled trial. Potential subjects for participation in this study will be identified by the Investigator based on their clinical and radiographic diagnosis of Alzheimer's disease, which will be completed as part of standard care. Up to 40 subjects will be enrolled. Subjects participating in the study will be randomized to receive either gummies containing L-Serine or placebo gummies, with the Investigator and study staff blinded to the group assignments. An individual subject's participation in the study will last approximately 40 weeks from time of enrollment. Study office visits will take place at Day 0, week 12, week 24 and week 36. Phone contact will be made at week 2, week 4 and week 8 to assess compliance, adverse events and concomitant medication. A follow-up phone call will also be made at week 40 to inquire about adverse events, concomitant medication, subject impression of study, subjective L-serine tolerability, and if they are continuing L-serine supplementation. If, due to study-related events, the PI judges that a participant should be seen in office during study participation, a visit will be scheduled (Unscheduled Visit)

The Day 0 visit includes subject consent, administration and scoring of the Clinical Dementia Rating Scale, review of medical history including any family history of Alzheimer's disease, a brief neurological and physical exam, capture and grading of baseline conditions, and a review of concomitant medications. Hemoglobin A1C, safety labs (CBC, BMP) and research only blood draw will be completed. Eligibility will be confirmed by the PI prior to randomization. If a participant fails to qualify based on their CDR score or Hgb A1 level, the portion of their blood drawn for research only will be discarded.

All subsequent study visits include a brief physical/neurological exam, adverse event assessment, study medication compliance assessment, concomitant medications review, safety blood draws (CBC, BMP) and research-specific blood draws.

Study medication will be dispensed at Day 0, week 12, and week 24, and collected at week 12, week 24 and week 36. All unused study drug will be collected and returned to the study sponsor.

The MoCA will be performed at Visits 0, week 24, week 36, and at early withdrawal or unscheduled visits. Three different MoCA versions will be administered in a random order during these assessments.

At week 24 and week 36, we propose to utilize a portion of the blood sample to examine neurally derived blood exosomes as potential biomarkers. Exosomes are a class of endosome-derived membrane vesicles which are shed by neural cells and transported in blood plasma. Thus, they provide an accessible measure of proteins excreted by neuronal cells. Since two proteins, phosphorylated tau and beta-amyloid-42, are implicated in the formation of neurofibrillary tangles and amyloid plaques, they can potentially be used as biomarkers of disease status. Fiandaca et al. (2015) found that the concentrations of phosphorylated tau and beta-amyloid present within exosomes were significantly higher for AD patients than case controls and that they increased progressively with time and disease progression. We propose to examine, in this proof-of-concept trial, if these exosome biomarkers change as a result of L-serine treatment. Furthermore, we will assess whether the concentrations or presence of these biomarkers show any correlation with cognitive decline.

3.2 Primary Endpoint

This proof-of-concept trial will assess the MoCA score at the week 36 study visit in patients with L-serine treatment compared to placebo. Slopes reflecting the change in MoCA score from Day 0 to the week 36 visit will be compared between treatment and placebo groups.

3.3 Secondary Endpoints

The Institute of Ethnomedicine will also assess plasma neurally derived exosome protein levels of beta-amyloid, as a biomarker which may be related to cognitive decline in eAD (Fiandaca et al. 2015). Slopes reflecting the change in biomarker protein level will be compared between treatment and placebo groups. In addition, we will assess the relationship between the MoCA scores and the concentration of plasma neuronal derived exosome biomarkers (Fiandaca et al. 2015) to demonstrate that this biomarker is related to cognitive decline, and that the MOCA assessment and neural exosome biomarkers are useful for future studies.

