6.1 Visit 1: Screening and Enrollment (Day 0)

- Obtain Informed Consent
- Clinical Dementia Rating Scale
- Brief review of medical history and demographic collection
- Neurological and physical exam
- Capture and grade baseline conditions
- Concomitant medication assessment
- Montreal Cognitive Assessment (MoCA)
- Blood Draw:
 - Safety Labs completed locally (BMP, CBC)
 - Hemoglobin A1C level
 - Samples sent to the Brain Chemistry Laboratories for L-serine levels and neurally-derived exosomes with optional excess blood set aside for future protein expression and RNA blueprints
- Review of Inclusion/Exclusion Criteria
- Randomization
- Dispense study medication, dosing instructions and calendar

6.2 Follow-Up Phone Call #1: Week 2

- Medication Compliance
- Adverse Events
- Concomitant Medications

6.3 Follow-Up Phone Call #2: Week 4

- Medication Compliance
- Adverse Events
- Concomitant Medications

6.4 Follow-Up Phone Call #3: Week 8

- Medication Compliance
- Adverse Events
- Concomitant Medications

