7.1 Sample Size Determination

In a previous study (Fiandaca, 2014), the neurally derived blood exosomal beta-amyloid protein level of eAD patients had a standard deviation of 2.8 pg/ml. The minimum detectable difference in the means of the treatment and placebo subjects is 2.5 pg/ml, with power 0.8 ($\alpha = 0.05$). An increase of approximately 7 pg/ml was observed between preclinical AD and AD patients (Fiandaca, 2014).

Based on Nasreddine et al. (2005), the standard deviation of the MoCA is approximately 4 points. Power calculations suggest that the minimum detectable difference in mean MoCA scores for two groups, each with 20 patients, is 3.65 points. A similar result for sample size comes from Mead's resource equation to predict adequate sample size, e.g. $E = N - B - T$, where N is the required sample size, E is the degrees of freedom of the error component (usually around 20), B is the blocking component for environmental effects, and T is the number of Treatments plus controls,

Placebo: 20 patients

L-serine: 20 patients

Total treatments: 2

Total patients: 40

Subtracting one degree of freedom from each value before inserting it in the equation, we have $E = 39 - 1 - 1 = 37$, Understanding that individual patients may drop out of the study before the 36 week dosing completion for various reasons, this sample size will be adequate to provide the needed statistical power.

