7.2 Statistical Methods

Nonparametric statistics are proposed since it is not known in advance if MoCA scores or levels of neurally-derived exosomes will approximate, or can be transformed, to a normal distribution. A Mann-Whitney U-test will compare exosomal protein levels or MoCA scores between the L-serine treatment and placebo patients at a $p < 0.05$ level. Parametric equivalents will be considered if appropriate to the distribution of the data.

First, we will check the effectiveness of the randomization by comparing the baseline characteristics of the L-serine and placebo groups according to demographic factors (e.g. age, gender). We will also assess whether the levels of biomarkers or cognitive impairment in the treatment group differ from the placebo group at time zero. This first test will check whether the randomization procedures were sufficient for the study. Next we will compare the exosomal protein levels or MoCA scores at the last study visit (month 9). (H_0 = there is no difference between the median exosomal protein level or MoCA score for treatment patients and control patients; H_1 = there is a difference between the median exosomal protein level MoCA score for treatment patients and control patients). A Mann-Whitney U-test will examine exosomal protein levels or MoCA scores of each patient, by comparing median values between groups. Second, we will assess the slope of the exosomal protein levels or MoCA scores over time to see if they differ among the treatment and control groups by Mann-Whitney U-test. We will use Spearman's Rank correlation, in which rho is the equivalent of the parametric correlation coefficient, to determine if there is a monotonic relationship between levels of proteins in the neurally-derived exosomes and the MoCA scores.

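### Exosomal beta-amyloid is to be compared only as an unadjusted month-9 level and as a slope; adjusting the week-36 level for the scheduled Day-0 level would recover up to about 9 points of power, depending on a correlation the documents do not give.

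*Combined protocol and SAP*

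**What the plan says.** Beta-amyloid in neurally derived exosomes is the secondary efficacy endpoint. Section 3.3 describes its between-arm comparison in one sentence: "Slopes reflecting the change in biomarker protein level will be compared between treatment and placebo groups".

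Section 7.2 sets out two between-arm tests. The first is at the last visit (month 9): "A Mann-Whitney U-test will examine exosomal protein levels or MoCA scores of each patient, by comparing median values between groups". The second is a Mann-Whitney test of slopes over time. Parametric equivalents are allowed if the distribution permits, but no covariate is named. The Day-0 value has one further use, as a check on the randomization: "We will also assess whether the levels of biomarkers or cognitive impairment in the treatment group differ from the placebo group at time zero". The plan does not say what follows if the arms differ.

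The Visit 1 list in section 6.1 includes the Day-0 sample: "Samples sent to the Brain Chemistry Laboratories for L-serine levels and neurally-derived exosomes with optional excess blood". Section 6.9 lists exosome samples at all four visits. Two other places disagree. Section 3.1 speaks of exosomes at weeks 24 and 36 only, and the Visit 2 list in section 6.5 names L-serine levels but no exosomes.

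Section 7.1 gives the planning figures: "the neurally derived blood exosomal beta-amyloid protein level of eAD patients had a standard deviation of 2.8 pg/ml", and "The minimum detectable difference in the means of the treatment and placebo subjects is 2.5 pg/ml, with power 0.8".

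**The concern.** The two planned tests treat the Day-0 level in opposite ways. The level test gives it a weight of zero. The slope takes it off with a weight fixed by the visit times. Either can be close to efficient or well short of it, depending on how strongly a patient's Day-0 and week-36 levels are correlated. The documents do not give that correlation, and section 7.2 does not say which of the two tests is the main one. A regression of the week-36 level on arm and Day-0 level estimates the weight from the data and needs no such guess.

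Chance imbalance also matters with 20 patients per arm. Under the level test, a Day-0 difference between the arms carries into the month-9 contrast in proportion to rho.

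This biomarker is one of the two efficacy readouts named in section 2. It is also the only endpoint for which section 7.1 states a power explicitly, and section 3.3 wants it to inform later studies.

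**Working it through.** **Inputs.** From section 7.1: SD 2.8 pg/ml, difference 2.5 pg/ml, power 0.8, alpha 0.05. The beta-amyloid sentence gives no sample size, so I take the 20 per arm listed in the same section. The test is two-sided because the alternative in section 7.2 has no direction: "there is a difference between the median exosomal protein level MoCA score for treatment patients and control patients". Assumed, because the documents are silent: rho, shown over a range; equal SDs at all visits; equal correlations between visits; normal data; an effect that grows linearly to 2.5 at week 36; no dropout.

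**The plan's own figure.** The standard error of the difference is 2.8 × sqrt(2/20) = 0.885. Power at 2.5 pg/ml is 80.6% by the normal approximation and 78.6% by noncentral t with 38 df. The stated 2.5 pg/ml reproduces.

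**Variance under each analysis, relative to 2.8².**
- Month-9 level: 1.
- Three-visit slope (weeks 0, 24, 36), scaled to 36 weeks: the mean time is 20 and the sum of squares is 400 + 16 + 256 = 672, so the factor is (36²/672)(1 − rho) = 1.929(1 − rho).
- Four-visit slope (weeks 0, 12, 24, 36): the sum of squares is 324 + 36 + 36 + 324 = 720, so the factor is 1.8(1 − rho).
- ANCOVA on Day 0: 1 − rho² = (1 − rho)(1 + rho), with 37 df.

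The three-visit slope beats the level once 1.929(1 − rho) < 1, that is, above rho of about 0.48. Leaving aside the one degree of freedom, ANCOVA beats the three-visit slope while 1 + rho < 1.929 (rho below about 0.93) and the four-visit slope while 1 + rho < 1.8 (rho below 0.8).

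**Power by noncentral t at 2.5 pg/ml.**

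| rho | Level | Three-visit slope | ANCOVA | ANCOVA minus better planned test |
|---|---|---|---|---|
| 0.3 | 78.6% | 65.8% | 82.2% | 3.6 |
| 0.5 | 78.6% | 80.0% | 88.8% | 8.8 |
| 0.7 | 78.6% | 95.1% | 97.1% | 1.9 |

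The last column is taken before rounding. On the same basis it is 1.6 points at rho 0.2, 6.5 at 0.4, 5.1 at 0.6 and 0.2 at 0.8. With four visits, slope power at rho 0.5 is 82.6%, and the gap falls to about 6 points.

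**Rank form, by simulation (6,000 trials per value of rho).**

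| rho | Mann-Whitney level | Mann-Whitney three-visit slope | Rank ANCOVA |
|---|---|---|---|
| 0.3 | 76.7% | 63.9% | 78.7% |
| 0.5 | 76.9% | 77.5% | 86.3% |
| 0.7 | 76.4% | 93.8% | 94.7% |

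A second simulation, with Quade's form of rank ANCOVA, gave 78.8% against 76.1% (level) at rho 0.3, 84.9% against 77.6% (slope) at 0.5 and 94.4% against 94.1% (slope) at 0.7. Taken together, the gain over the better planned test is roughly 3, 8 and 1 points. With a four-visit slope at rho 0.7 the order reverses slightly: 95.3% for the slope against 94.4% for rank ANCOVA. In a separate simulation under no effect, with 4,000 trials at rho 0.5, rejection rates were 4.3% to 5.1% across the methods.

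**Chance imbalance.** The standard error of the Day-0 difference is also 0.885 pg/ml, over a third of 2.5. At an assumed rho of 0.5, a one-standard-error imbalance moves the level contrast by 0.5 × 0.885 = 0.44 pg/ml.

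**The case against.** The strongest reply is that the plan runs both tests, so the fair comparator is the better of the two. On that basis the loss is modest and nearly vanishes at high rho. This stands, and it sets the size given here. A gap of 18 to 19 points can be found at rho 0.7, but only against the level test, when the planned slope already has 95% power. The reply is not complete, though. Section 7.2 does not say which test leads, rho is unknown beforehand, and choosing the lead test after seeing both results would inflate the type I error.

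A reader might infer three stronger things.
- That the plan forfeits about 10 points of power as a fixed fact. A loss near that size needs rho near 0.5, which the documents do not state, and it is about the maximum against the better planned test.
- That the baseline is discarded. The slope uses it; the shortcoming is a fixed rather than an estimated weight.
- That adjustment wins under every schedule and correlation. It does not if the slope uses all four visits in section 6.9 and rho is high.

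It is also fair to say that this is a secondary endpoint in a 40-patient Phase IIa trial, and that section 7.2 prescribes the same two tests for MoCA in the same sentences. Both are true. They limit the weight of the point but do not remove it.

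**Conclusion.** The point holds as a low-cost gain in efficiency and robustness. It does not make the planned tests invalid: their simulated type I error is close to 5%. No baseline-adjusted beta-amyloid analysis is planned although Day-0 samples are scheduled. At the plan's own 2.5 pg/ml the cost against the better planned test is about 0 to 9 points of power over rho 0.2 to 0.8, with the peak near 0.5. Against the slope alone, the only comparison named in section 3.3, it is about 16, 9 and 2 points at rho 0.3, 0.5 and 0.7.

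These sizes rest on the assumptions listed above. The 2.8 is a cross-sectional SD from an earlier study, applied here to every visit, and any dropout would lower all the powers. The point also depends on the Day-0 assay being done. Sections 6.1, 6.9 and 7.2 point that way, but section 3.1 does not. The change should be made, but the trial does not stand or fall on it.

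**What to change.** In sections 3.3 and 7.2, name one main beta-amyloid comparison: the week-36 level between arms with the Day-0 level as covariate. Use ANCOVA on a suitable scale (for example log levels, if residuals allow), or rank ANCOVA for the test if the nonparametric intent is to be kept. Report the adjusted difference with a 95% CI from the ANCOVA. Keep the slope comparison as supportive, and state which visits enter it and how it is computed.

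Reconcile section 3.1 (weeks 24 and 36 only) and section 6.5 (no exosomes at Visit 2) with sections 6.1 and 6.9, so that the Day-0 assay is assured. The same edit to section 7.2 is the natural place to consider the MoCA analysis, which shares its wording.

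The cost is SAP wording and one model on samples already scheduled. The downside is one degree of freedom and, for rank ANCOVA, a less direct effect scale, which the ANCOVA estimate covers.
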